1.1 Scope of document

The RAP documents contain detailed information to aid the production of Statistics & Programming input into the Clinical Study Report (CSR) for trial “**CCJM112X2203**”.

The Statistical analysis plan (SAP) describes the implementation of the statistical analysis planned in the protocol.

Tables, Figures, Listings (TFL) details the presentation of the data, including shells of summary tables, figures and listings, and Programming Datasets Specification (PDS) contains programming specifications e.g. for derived variables and derived datasets, to support the creation of CSR outputs.

1.2 Study reference documentation

Final study protocol (v02) is available at the time of finalization of this Statistical Analysis Plan amendment v01.

1.3 Study objectives

1.3.1. Primary objective(s)

Primary objective(s)	Endpoints related to primary objectives

To assess the efficacy of CJM112 versus placebo on facial inflammatory lesion counts in patients with moderate to severe inflammatory acne.	
Total inflammatory facial lesion count at week 12.

1.3.2. Secondary objective(s)

Secondary objective(s)	Endpoints related to secondary objective(s)

To assess the safety and tolerability of CJM112 in patients with moderate to severe inflammatory acne.	
Number and severity of AEsSafety and tolerability assessments including general safety parameters (laboratory parameters, physical examination, vital signs, ECG) assessed at baseline and repeatedly until study completion visit.

To assess the PK of CJM112 in patients with moderate to severe acne.	
$C_{min,ss}$ (multiple doses) from serum concentration data (non-compartmental analysis).

Corporate Confidential Information

1.4 Study design and treatment

This is a randomized, placebo controlled, subject and investigator blinded, multi-center, non- confirmatory, parallel group, proof of concept study in patients with moderate to severe inflammatory acne. After an initial screening period (up to 4 weeks), the study is conducted in 2 consecutive treatment periods, each of 12 weeks, to show clinical efficacy (in treatment period 1) and potential sustainability of response (in extension period 2). At the beginning of treatment period 1, patients will be randomized to one of 3 treatment groups for the first 12 weeks only:

1. CJM112 at monthly intervals,
2. CJM112 at monthly intervals,
3. Placebo s.c. at monthly intervals.

At the end of treatment period 1, all patients will be offered to the opportunity to remain in the study for the extension period 2. Patients who enter extension period 2 will receive the following treatments:

- Treatment Period 1, . Extension Period 2,
- Treatment Period 1, Extension Period 2,
- Treatment Period 1, Placebo. Extension Period 2, via re-randomization with a randomization ratio of 1:1.

Therefore, exposure to placebo will be limited to a maximum of 12 weeks (treatment period 1). To keep the blinding at each time point, 3 injections will be given.

Whether patients continue or do not continue into extension period 2, all patients will be followed up for safety and potential sustainability of efficacy, for an additional 13 weeks without any treatment.

Figure 1-1: Study design

2 First interpretable results (FIR)

First interpretable results (FIR) will be provided for this trial.
Corporate Confidential Information

Corporate Confidential Information

Corporate Confidential Information

4 Statistical methods: Analysis sets

For all analysis sets, patients will be analyzed according to the study treatment(s) received. This implies that for patients for whom the actual treatment received does not match the randomized treatment, the treatment actually received will be used for the analysis.

All patients who received at least one dose of any study drug will be included in the safety data analysis “safety population”.

The PK analysis set will include all patients with at least one available valid (i.e., not flagged for exclusion) PK concentration measurement, who received any study drug and experienced no protocol deviations with relevant impact on PK data.

All patients with evaluable PD parameter data and no major protocol deviations impacting PD data will be included in the PD data analysis “PD population”.

The analysis sets and protocol deviation codes are related as follows:

Table 4-1 Protocol deviation codes and analysis sets

Category Deviation code	Text description of deviation	Data exclusion
Patients are excluded from all (safety) analysis in case of these PDs:		Exclude patient completely from all (safety) analysis sets
Patients are excluded from PK analysis in case of these PDs:		Exclude patient from PK analysis set
Patients are excluded from PD analysis in case of these PDs:		Exclude patient from PD analysis set

Category	Text description of deviation	Data exclusion
Deviation code		
	Patients are excluded from PK and PD analysis in case of these	
	PDs:	
		Exclude patient from PK
		and PD analysis sets

If updates to this table are needed, an amendment to the SAP needs to be implemented prior to DBL.

5 Statistical methods: Group presentations

For the analysis plan here onwards, treatment groups are defined as below and these groups will be followed for most summary tables by period and treatment group, unless otherwise stated.

- Period 1 (P1, up to and including Visit 201): Treatment group for Period 1 i.e.:
 - CJM112
 - CJM112
 - and Placebo.
- Extension Period 2 (P2, from Visit 201 onwards) and post-treatment follow-up: Treatment sequence for the people participating in the extension i.e.:
 - CJM112 CJM112
 - CJM112 CJM112
 - Placebo/ CJM112
 - Placebo/ CJM112

For the summary statistics when performed by period and summary plots (such as mean plots and boxplots), unless otherwise stated, Visit 201 will be included in both P1 and P2; the “Post-treatment Follow-up” epoch will be summarized together with P2.

Patients not entering P2 and proceeding directly to follow-up, unless stated otherwise, will also be summarized for alone (without patients entering Period 2) in a table including all their P1 assessments and follow-up assessments. Respective summary plots are not planned but may be provided, if deemed necessary by the team.

Individual (Spaghetti) plots over time will be performed, unless otherwise stated, by sequence and will include the whole duration of the study.

6 Statistical methods for Pharmacokinetic (PK) parameters

All patients within the PK analysis set will be included in the PK data analysis.

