6.6 Permitted dose adjustments and interruptions of study treatment

Study treatment dose adjustments and/or interruptions are not permitted. Occasional interruptions in study treatment must be recorded as protocol deviations.

These changes must be recorded on the Dosage Administration Record Case Report Form (CRF).

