11.1 Analysis sets

For all analysis sets, subjects will be analyzed according to the study treatment(s) received.

The safety analysis set will include all subjects that received any study drug.

The PK analysis set will include all subjects with at least one available valid (i.e. not flagged for exclusion) PK concentration measurement, who received any study drug and with no protocol deviations that impact on PK data.

The PD analysis set will include all subjects with available PD data and no protocol deviations with relevant impact on PD data.

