11.4.3 Handling of missing values/censoring/discontinuations

All patients with available data after baseline and until Week 12 will be included in the primary analysis. The primary analysis model is known to give unbiased results under the assumption that missing data are at random (MAR), i.e. given observed data the missingness does not depend on unobserved data. If a patient drops out the study according to the predefined discontinuation criteria ([Section 7.2](#)), this MAR assumption remains valid. Besides, last observation carried forward (LOCF) method will be used in a sensitivity analysis to handle missing data.

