6.2 Descriptive analyses

CJM112 serum concentrations ($\mu\text{g/mL}$) will be listed by treatment group, patient, and visit/sampling time point. Descriptive summary statistics will be provided by treatment group and visit/sampling time point. Summary statistics will include mean (arithmetic and geometric), SD, CV (arithmetic and geometric), median, minimum, maximum, and the frequency (n, %) of concentrations below the LLOQ. Concentrations below LLOQ will be treated as zero in summary statistics and for PK parameter calculations. A geometric mean will not be reported if the dataset includes zero values.

Pharmacokinetic parameters will be listed by treatment group and patient, and summarized by treatment with descriptive statistics as listed above. Graphical methods will be employed to show mean and individual concentration-time profiles over the whole study by treatment sequence, with time defined as visit and actual day respectively.

7 Statistical methods for Pharmacodynamic (PD) parameters

All patients within the PD analysis set will be included in the PD data analysis.

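### The population for the primary Week 12 lesion-count analysis is stated in two unreconciled ways, and on either one patients are grouped by treatment received rather than as randomised

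*SAP*

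**What the plan says.** **PD set.** SAP Section 7 contains the primary lesion-count analysis (7.1) and opens with "All patients within the PD analysis set will be included in the PD data analysis". SAP Section 4 defines that set: "All patients with evaluable PD parameter data and no major protocol deviations impacting PD data will be included in the PD data analysis". The action in SAP Table 4-1 applies to the whole patient: "Exclude patient from PD analysis set". Protocol 11.1 describes the same set without requiring that a deviation be major: "The PD analysis set will include all subjects with available PD data and no protocol deviations with relevant impact on PD data".

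**All patients with data.** Protocol 11.4.3 states "All patients with available data after baseline and until Week 12 will be included in the primary analysis", and SAP 7.1.4 repeats the sentence. Neither section refers to the PD set or to deviations.

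**Grouping.** Protocol 11.1 says "For all analysis sets, subjects will be analyzed according to the study treatment(s) received". SAP Section 4 has the same rule and spells it out: "for patients for whom the actual treatment received does not match the randomized treatment, the treatment actually received will be used for the analysis".

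The only sets defined in the visible text are safety, PK and PD. None of the visible sensitivity or supportive analyses (Protocol 11.4.3 and 11.4.4; SAP 7.1.4 to 7.1.6) groups patients as randomised.

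**The concern.** A patient who has post-baseline counts and a PD-relevant deviation is in the primary analysis under one rule and out under the other. With about 21 completers per arm, a few such patients can move the estimate to which the efficacy criteria are applied.

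Deviations happen after randomisation and may depend on response. Topical acne products are restricted in treatment period 1 (Protocol 4.2 and 5.2), and a patient doing badly has more reason to use them. Under Protocol 7.2, prohibited treatment only might lead to discontinuation, so such a patient can stay and contribute counts. Protocol 6.6 adds another source: "Occasional interruptions in study treatment must be recorded as protocol deviations". Whether either kind of deviation leads to exclusion cannot be seen, because the deviation codes in Table 4-1 are not visible.

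Grouping by treatment received is usual for safety and PK. For the primary efficacy contrast it gives up the protection of randomisation whenever someone is mis-dosed, and here it applies whichever population is meant.

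**Working it through.** **1. The passages compared**

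| Question | SAP 4 and opening of 7 | Protocol 11.1 | Protocol 11.4.3 and SAP 7.1.4 |
|---|---|---|---|
| Who is in? | Evaluable PD data | Available PD data | Any data after baseline to Week 12 |
| Removed for deviations? | Yes, major ones impacting PD data | Yes, those with relevant impact (not limited to major) | Not mentioned |
| Grouped by | Treatment received | Treatment received | No set named, so the general rule applies: treatment received |

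No visible text gives precedence or says that one population is nested in the other.

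**2. Reproducing the plan's operating characteristics**

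Inputs: SD 0.47 on the log scale, looks at 10+10 and 21+21, true effects of 0 and 40% (0.511) (Protocol 11.7 and Table 11-1). Go requires at least 90% posterior probability of being better than placebo and at least 50% probability of an effect of 0.357 or more. Futility requires at least 60% probability of being worse (Protocol synopsis). I used a normal approximation with a flat prior and known SD.

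- SE at look 1 = 0.47 × √(2/10) = 0.210. SE at look 2 = 0.47 × √(2/21) = 0.145.
- Correlation of the looks = 0.145/0.210 = 0.690.
- Go cut = max(0.357, 1.2816 × SE). The second term is 0.269 and 0.186, so the cut is 0.357 at both looks.
- Futility cut at look 1 = −0.2533 × 0.210 = −0.053.

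| | Computed | Table 11-1 |
|---|---|---|
| Look 1, go at effect 0 | 4.5% | 5% |
| Look 1, futility at effect 0 | 40.0% | 40% |
| Look 1, go at 40% | 76.8% | 77% |
| Either look, go at effect 0 | 4.75% | 5% |
| Either look, go at 40% | 90.3% | 90% |

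The second row of Table 11-1 matches on the cumulative reading. The final look alone would give 0.7% and 86%. The plan's figures are not in dispute.

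**3. Illustration of selective exclusion**

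Assumption: about 10% of one arm only (2 of 21) is excluded, and those patients have higher log counts than their arm's mean. This rate and these differences are not in the documents.

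- Excluded patients *d* SD worse: shift = 2 × *d* × 0.47/19 = 0.025 (*d* = 0.5) or 0.049 (*d* = 1).
- Exactly the worst 10%: shift = 0.47 × φ(1.2816)/0.9 = 0.092.

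The shift is added to the contrast if the exclusions are from the active arm and subtracted if they are from placebo. SE is held unchanged, and bivariate normal probabilities are used.

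| | None excluded | 0.5 SD worse | 1 SD worse | Worst 10% |
|---|---|---|---|---|
| Active arm, effect 0, both looks: false-go | 4.8% | 6.1% | 7.8% | 11.6% |
| Placebo arm, effect 40%, both looks: go | 90.3% | 87% | 84% | 76% |
| Active arm, effect 0, final look only: false-go | 4.8% | 5.0% | 5.3% | 6.5% |
| Placebo arm, effect 40%, final look only: go | 90.3% | 88% | 86% | 83% |
| Active arm, effect 0, single look at 21 per arm: false-go | 0.7% | 1.1% | 1.7% | 3.4% |
| Placebo arm, effect 40%, single look at 21 per arm: go | 86% | 81% | 76% | 67% |

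The worst-10% column uses a truncated-normal mean and is an upper extreme. Simulating the actual removal of the worst 1 of 10 and worst 2 of 21 (400,000 runs) gives 10.6% false-go and 78.3% go over both looks.

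**4. Exclusions unrelated to outcome**

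Removing 2 patients per arm at random (n = 19) lowers the cumulative go chance at 40% only from 90.3% to 89.3% and leaves false-go at 4.8%. The risk is therefore bias rather than lost numbers.

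**The case against.** The strongest reply is that the two rules nest. The sentence about all patients with data sits under missing values in the protocol and model checking in the SAP, and it leads straight into MAR and LOCF. It may mean only that completers are not required, within the PD set already named. That is a fair reading, but it is the narrower of the two above, no visible text states it, and taken literally the sentence includes deviators.

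Other points have some force:

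- If no Table 4-1 deviation applies to a patient with post-baseline counts, the two populations coincide. The codes are not visible, so this cannot be excluded. Some SAP text is also blacked out, so the absence of an as-randomised set is a statement about visible text only.
- Sites are blinded (Protocol 6.4), deviations are determined before lock and unblinding (Protocol 10.3), and changes to Table 4-1 need a SAP amendment before lock. This limits manipulation and makes strongly one-sided exclusion less likely. Trimming both arms equally gives no shift.
- Patients discontinued for worsening on the investigator's global assessment fall under the MAR statement, so deviators need not be the worst responders.
- The study is non-confirmatory and its criteria guide rather than bind. Allocation through the interactive system should make mis-dosing uncommon, and grouping by treatment received is a stated choice, consistent across both documents.

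These points lower the likely size. They neither say which population is primary nor restore the randomised comparison.

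**Conclusion.** The point holds and should be fixed. The inconsistency and the grouping rule are established from the text alone and do not depend on the illustration.

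The practical size cannot be computed, because the documents give no deviation or mis-dosing rate. The figures above rest on an assumed 10% exclusion in one arm only, linked to response, and run from almost no effect to roughly a doubling of the false-go chance. Bias could go in either direction. The effect of grouping by treatment received is not quantified.

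**What to change.** Define the primary efficacy set as all randomised patients with a baseline and at least one post-baseline facial inflammatory lesion count up to Week 12, analysed by randomised arm, with no exclusion for deviations. Report by arm how many randomised patients fall outside it.

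Keep the PD set, by treatment received, as a sensitivity analysis of the same model. Keep treatment received for safety and PK.

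Amend Protocol 11.1 and SAP Sections 4 and 7 to agree with Protocol 11.4.3 and SAP 7.1.4, and use one wording of the deviation criterion (major or not) in both documents. Make the changes before database lock.

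Cost: protocol and SAP wording plus one extra analysis run. No new data are needed.

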6.1 Variables

The following pharmacokinetic parameters will be determined using the actual recorded sampling times and non-compartmental method(s) with Phoenix WinNonlin (Version 6.2 or higher): Cmin,ss from the serum concentration-time data.

6.2 Descriptive analyses

CJM112 serum concentrations ($\mu\text{g/mL}$) will be listed by treatment group, patient, and visit/sampling time point. Descriptive summary statistics will be provided by treatment group and visit/sampling time point. Summary statistics will include mean (arithmetic and geometric), SD, CV (arithmetic and geometric), median, minimum, maximum, and the frequency (n, %) of concentrations below the LLOQ. Concentrations below LLOQ will be treated as zero in summary statistics and for PK parameter calculations. A geometric mean will not be reported if the dataset includes zero values.

Pharmacokinetic parameters will be listed by treatment group and patient, and summarized by treatment with descriptive statistics as listed above. Graphical methods will be employed to show mean and individual concentration-time profiles over the whole study by treatment sequence, with time defined as visit and actual day respectively.

7 Statistical methods for Pharmacodynamic (PD) parameters

All patients within the PD analysis set will be included in the PD data analysis.

7.1 Primary objectives

The primary aim of this study is to assess the efficacy of CJM112 versus placebo on inflammatory facial lesion counts in patients with moderate to severe inflammatory acne in Period 1.

7.1.1 Variables

The primary variable is the natural log transformed total inflammatory facial lesion counts. Baseline is defined as the Visit 101 assessment.

7.1.2 Descriptive analyses

The primary variable will be listed by treatment sequence, patient, period and visit/time, and descriptive statistics will be provided, for raw, change from baseline and percentage change from baseline, by period, treatment group and visit/time. Summary statistics will include mean (arithmetic and geometric), SD, CV (arithmetic and geometric), median, minimum, maximum; geometric mean and its CV will only be provided for the raw values.

Graphical methods will be employed to show geometric mean and individual (Spaghetti) plots over time.

7.1.3 Statistical model, assumptions and hypotheses

The log transformed inflammatory facial lesion count will be analyzed using a Bayesian model for repeated measurements. The model will include effects including log transformed baseline inflammatory facial lesion count, treatment group, visit, treatment group by visit interaction and

log transformed baseline inflammatory facial lesion count by visit interaction. A non-informative prior will be utilized to obtain the posterior estimates and an unstructured covariance will be assumed. Other factors such as gender and race may also be explored if the distribution per factor is reasonably balanced. The log transformed baseline will be centered and standardized before used in the model.

Corporate Confidential Information

The posterior estimates of the treatment effect and the treatment difference (along with its 90% credibility interval) at each visit (with Week 12 being of primary interest) will also be provided. The results will be reported in terms of ratio of geometric means by back transforming the estimates from the log-scale.

7.1.4 Model checking procedures

All patients with available data after baseline and until Week 12 will be included in the primary analysis. The primary analysis model is known to give unbiased results under the assumption that missing data are at random (MAR), i.e. given observed data the missingness does not depend on unobserved data. If a patient drops out of the study according to the predefined discontinuation criteria (Protocol Section 7.2), this MAR assumption remains valid. Besides, last observation carried forward (LOCF) method will be used in a sensitivity analysis to handle missing data.

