7.2 Discontinuation of study treatment

Individual Treatment Discontinuation Rules

Patients may voluntarily discontinue the study for any reason at any time. The investigator must discontinue study treatment for a given subjects, if, on balance, he/she believes that continuation would be detrimental to the patient's well-being.

Study treatment **must** be discontinued under the following circumstances:

- Patient withdraws consent
- Pregnancy
- Emergence of the following AEs (CTCAE grading v4.03):
 - Grade 3 or higher allergic or hypersensitivity reaction
 - Acute, grade 3 or higher infection as judged by the investigator
 - Neutropenia grade 3 or higher
- Clinical worsening of acne (worsening of at least one grade in the IGA, e.g. from severe to very severe) and/or any active ongoing scarring as per investigator judgement
- Any other protocol deviation that results in a significant risk to the patient's safety

Use of prohibited treatment as per [Section 5.2](#) might result in treatment discontinuation (decision will be taken on case by case basis after consultation with Sponsor).

The appropriate personnel from the site and Novartis will assess whether treatment should be discontinued for any patient whose treatment code has been broken inadvertently for any reason.

Subjects who discontinue study treatment should NOT be considered withdrawn from the study UNLESS they withdraw their consent. Where possible, they should return for the assessments as defined in the [Assessment table](#) for the post-treatment follow-up visits.

If they fail to return for these assessments for unknown reasons, every effort (e.g. telephone, e-mail, letter) should be made to contact them as specified in [Section 7.1](#).

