7.3 Withdrawal of informed consent

Patients may voluntarily withdraw consent to participate in the study for any reason at any time.

Withdrawal of consent from the study is defined as when a patient:

- Does not want to participate in the study anymore and
- Does not want any further visits or assessments and
- Does not want any further study related contacts and
- Does not allow analysis of already obtained biologic material.

In this situation, the investigator must make every effort (e.g. telephone, e-mail, letter) to determine the primary reason for the patient's decision to withdraw his/her consent and record this information.

Study treatment must be discontinued and no further assessments conducted, and the data that would have been collected at subsequent visits will be considered missing.

Further attempts to contact the patient are not allowed unless safety findings require communicating or follow-up.

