11.4.2 Statistical model, hypothesis, and method of analysis

The log transformed inflammatory facial lesion count is expected to be approximately normally distributed. It will be analyzed using a Bayesian mixed effect model for repeated measures (MMRM), with log transformed baseline inflammatory facial lesion count as a covariate; treatment sequence, visit, treatment group by visit interaction and log transformed baseline inflammatory facial lesion count by visit interaction as fixed effects. A non-informative prior will be utilized to obtain the posterior estimates. Unstructured covariance structure will be used. Other factors such as gender and race will also be explored for statistical significance if the distribution per factor is reasonably balanced. The log transformed baseline lesion count will be centered and standardized before used in the model.

Data up to Week 12 will be included in the model, for the comparison of CJM112 versus placebo at Week 12, which is of primary interest. Corporate Confidential Information

Bayesian posterior probabilities will be used to assess the following criteria as a guide to decision making ([Fisch et al 2015](#)), though other criteria may be taken into account:

Corporate Confidential Information

The posterior estimates of the treatment effect and the treatment difference (along with its 90% credibility interval) at each visit (with Week 12 being of primary interest) will be provided. The results will be reported in terms of ratio of geometric means by back

transforming the estimates from the log-scale. Data will also be presented in graphics such as spaghetti plot.

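### MAR is stated as fact for exits under Protocol Section 7.2 when it is only assumed, and LOCF cannot show what departure would reverse a near-threshold pass

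*SAP*

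**What the plan says.** SAP 7.1.4 and Protocol 11.4.3 describe the primary repeated-measures model as unbiased if data are missing at random, meaning that missingness does not depend on unseen data once the observed data are given. The SAP then adds: "If a patient drops out of the study according to the predefined discontinuation criteria (Protocol Section 7.2), this MAR assumption remains valid". The protocol makes the same claim and names the one analysis aimed at missing data: "this MAR assumption remains valid. Besides, last observation carried forward (LOCF) method will be used in a sensitivity analysis to handle missing data".

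Protocol 7.2 opens with "Patients may voluntarily discontinue the study for any reason at any time". Its list of mandatory reasons for stopping includes consent withdrawal, pregnancy, certain adverse events and "Clinical worsening of acne (worsening of at least one grade in the IGA, e.g. from severe to very severe) and/or any active ongoing scarring", the last as judged by the investigator. It also says: "Subjects who discontinue study treatment should NOT be considered withdrawn from the study UNLESS they withdraw their consent". Only under withdrawal of consent (Protocol 7.3) does the plan say that "the data that would have been collected at subsequent visits will be considered missing".

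The visible model (Protocol 11.4.2, SAP 7.1.3) contains log baseline count, treatment, visit, their interactions and the repeated log counts. On which data enter, the protocol says: "Data up to Week 12 will be included in the model".

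**The concern.** A predefined exit rule makes data MAR only if the rule acts through data that the model conditions on. Several Section 7.2 reasons need not. Consent withdrawal can have any cause. Scarring is a judgement, and post-baseline IGA and adverse events are not in the model. Earlier lesion counts are a partial proxy for some of these, so MAR may be a fair working assumption, but the criteria do not secure it. Section 7.2 also mainly governs stopping treatment, so it cannot by itself settle why Week 12 counts are missing.

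The sensitivity analysis does not fill the gap. LOCF uses observed values only, so it does not vary with the size of any assumed departure from MAR. If the estimate falls just above the 30% threshold, a reader of the go/no-go result cannot tell from the primary model plus LOCF whether the pass depends on MAR.

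**Working it through.** **Inputs from the documents.** SD 0.47 on the log scale, about 21 completers per arm, dropout around 15%, and a design effect of 40% = 0.511 (Protocol 11.7 and Table 11-1). Efficacy requires at least 90% probability of any benefit and at least 50% probability of a benefit of at least 30%, or 0.357 (Protocol synopsis, Data analysis). The placebo fall is 20–30% (Protocol 3.7) or up to 30–40% (Protocol 3.2).

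**Assumed here.** A flat-prior normal approximation, the observed estimates shown, the timing and balance of dropout, and the form of any departure from MAR.

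**Step 1: reproduce Table 11-1.**
- SE = 0.47 × √(2/21) = 0.145, and 0.47 × √(2/10) = 0.210 at the first look.
- The 90% criterion needs 1.2816 × 0.145 = 0.186, or 1.2816 × 0.210 = 0.269 at the first look. Both are below 0.357, so the 30%/50% criterion decides.
- First look: pass 4.5% at no effect and 76.8% at 40%; futility 40% at no effect. The table gives 5%, 77% and 40%.
- Pass at either look, by simulation: 4.7% at no effect and 90.3% at 40%. The table gives 5% and 90%. At a true 30% effect the pass rate is about 63%.

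**Step 2: tipping points.** Suppose a fraction m is missing in each arm, and missing CJM112 patients have Week 12 log counts that exceed the MAR prediction by a net amount δ (CJM112 shift minus placebo shift). The estimate then falls by m × δ, and the pass reverses at δ* = (estimate − 0.357)/m. With half of the missing patients affected, m = 0.075.

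| MAR estimate | δ* at m = 0.15 | Excess count | δ* at m = 0.075 | Excess count |
|---|---|---|---|---|
| 0.38 | 0.023/0.15 = 0.153 | 17% | 0.307 | 36% |
| 0.40 | 0.043/0.15 = 0.287 | 33% | 0.573 | 77% |
| 0.45 | 0.093/0.15 = 0.620 | 86% | 1.24 | 3.5-fold |
| 0.511 | 0.154/0.15 = 1.027 | 2.8-fold | 2.05 | 7.8-fold |

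At 0.38 the margin is 0.023/0.145 = 0.16 SE, so sampling error matters more there than missing data.

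**Step 3: how often a pass lies near the threshold.** In the two-look simulation, the share of passes with a deciding estimate of 0.357 to 0.45 is 0.225/0.903 = 25% at a true 40% effect and 0.263/0.628 = 42% at a true 30% effect. With a single look it is 23% and 48%.

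**Step 4: what LOCF does when MAR holds.** Assume a linear fall in log count, all dropouts last seen at Week t, a MAR estimate of 0.40 and 15% dropout in both arms. LOCF then gives 0.40 × [1 − 0.15 × (1 − t/12)]:
- t = 2: 0.350 (fail)
- t = 3: 0.355 (fail)
- t = 4: 0.360 (pass)
- t = 8: 0.380 (pass)

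At t = 4 with dropout of 16% on CJM112 and 14% on placebo, LOCF gives 0.40 × (1 − 0.16 × 2/3) − p × 0.02 × 2/3 = 0.3573 − 0.0133p, where p is the placebo fall on the log scale. For falls of 20% to 40% (p = 0.223 to 0.511) this is 0.354 to 0.351 (fail). With 14%/16% it is 0.3627 + 0.0133p = 0.366 to 0.369 (pass). The LOCF outcome therefore follows dropout timing and balance.

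**Step 5: whether LOCF reacts when MAR fails.** An illustrative simulation used counts at Weeks 4, 8 and 12, with exit after Week 8 depending on the Week 8 count and also on the unseen Week 12 count (log-odds 1 to 2 per SD). Bias of the MAR estimate:
- 15%/15% missing: about 0
- 20%/10% missing (CJM112/placebo): +0.011 to +0.046
- 10%/20% missing: −0.012 to −0.046

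With equal dropout, the LOCF shift was about −0.020 whether or not MAR held.

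**The case against.** - **Reading of the sentence.** Both documents call MAR an assumption, and the disputed sentence is limited to predefined criteria. Exit for any reason precedes the bulleted list and is a patient right rather than a criterion. That is fair, but consent withdrawal and investigator-judged scarring are in the list, so the objection to the sentence survives.
- **What MAR requires.** An exit reason need not be a covariate for MAR to hold. Pregnancy or neutropenia has no stated link to unseen lesion counts, and IGA worsening is partly reflected in modelled counts. This supports MAR as an assumption, not as a guaranteed property.
- **Redaction.** Parts of Protocol 11.4.2 and of SAP 7.1.3 and 7.1.6 are blacked out, so a further missing-data analysis may exist. The point is confined to the visible text.
- **Assumed inputs.** The visit schedule is not visible, and the LOCF timings and simulation settings are illustrative. They show direction and order of size only.
- **LOCF can be conservative.** In one run with 20%/10% missing and a true effect of 0.40, the MAR estimate was 0.442 and LOCF gave 0.370. In another, with exit driven by the unseen Week 12 count on CJM112 only, 16% missing per arm and a true effect of 0.511, MAR gave 0.596 and LOCF 0.535, both too favorable. With CJM112-only mechanisms, the gap between LOCF and MAR was −0.060 when MAR held and −0.048 when it did not. LOCF does not diagnose the departure.
- **Materiality.** The largest bias in Step 5, 0.046, is 0.046/0.145 = 0.3 SE. The study is non-confirmatory and the criteria serve "as a guide to decision making". This stands and sets the priority.

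**Conclusion.** The concern holds. The claim that MAR is secured by the Section 7.2 criteria is unsupported, and LOCF cannot supply the missing information. The consequence is confined to estimates near 0.357. Between 0.38 and 0.45, net excess counts of 17% to 86% in the missing CJM112 patients would reverse a pass. At 0.511 the conclusion is robust, and equal departures in the two arms with equal dropout largely cancel. These figures rest on 15% missing per arm, the planned SD and a near-flat prior. If fewer patients lack Week 12 counts, for example because those who stop treatment return for assessment, the tipping points move further away. This is a low-priority improvement.

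**What to change.** 1. In SAP 7.1.4, replace the sentence with: *MAR is assumed; it is not guaranteed by the Section 7.2 criteria.* The same correction applies to Protocol 11.4.3 if it is next amended.
2. Keep LOCF and prespecify a delta-adjusted tipping-point analysis of the Week 12 log count, with the shift varied separately by arm for each dose comparison. Report the shifts at which the 30%/50% criterion fails. A grid from 0 to 1.1, defined as the average shift over all missing patients in an arm, covers every case in the table. The half-affected shifts of 1.24 and 2.05 are averages of 0.62 and 1.03.
3. As a minor clarification, state whether the available data up to Week 12 include counts taken after other anti-acne treatment. Protocol 3.7 expects such treatment for some patients who stop. Protocol Table 5-1 and the PD analysis set rules (Protocol 11.1, SAP Section 4) cover prohibited treatments and deviations, but do not clearly settle this for patients already off study treatment.

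The cost is one sentence and some extra runs on about four missing patients per arm (15% of 25), over a two-way grid for each of two doses. No visits or data are added. The downside is that a near-threshold result may look less secure.
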